1.0 TRIAL SUMMARY

Abbreviated Title	REPORT
Full title	REirradiation and PD-1 blockade On Recurrent squamous cell head and neck Tumors
Trial Phase	Phase I/II
Clinical Indication	Head and neck squamous cell carcinoma (HNSCC)
Trial Type	Exploratory
Type of control	NA
Route of administration	Intravenous
Trial Blinding	Open-label
Treatment Groups	Nivolumab, intravenous every 2 nd week (1 cycle = 2 weeks), dose escalation schedule (1.0, 3.0 mg/kg), for a maximum of 12 months or until disease progression. In addition radiotherapy (RT) will be given to a total dose of 60 Gy (1,5 Gy fractions twice daily) for a total period of 4 weeks
Number of trial subjects	20
Estimated enrollment period	Q2 2017 – Q4 2018
Estimated duration of trial	The sponsor estimates that the trial will require approximately 2.5 years from the time the first subject signs the informed consent until the last subject's last on-treatment visit. Follow-up will continue 4 years after end of study therapy.
Duration of Participation	Each subject will participate in the trial until death, drop out, or loss-to follow-up from the time the subject signs the Informed Consent Form (ICF) through the final contact. After a screening phase of up to 28 days, each eligible subject will receive nivolumab. Two weeks after start of nivolumab the patients will receive radiotherapy (RT) to a total dose of 60 Gy, given as 1.5 Gy fractions twice daily for a total period of 4 weeks. Treatment with nivolumab will continue until disease progression, unacceptable adverse event(s), intercurrent illness that prevents further administration of treatment, Investigator's decision to withdraw the subject, noncompliance with trial treatment or procedures requirements, subject receives nivolumab for 12 months, pregnancy, or administrative reasons. After the end of treatment, each subject will be followed for 30 days for adverse event monitoring (serious adverse events [SAEs] will be collected for 90 days after the end of treatment). Patients without disease progression will have follow-up visits for 4 years after end of study therapy.

2.0 BACKGROUND AND RATIONALE

2.1 Rationale for study therapy

Radiotherapy (RT) is a main treatment modality across different cancer forms and is administered to approximately 50 % of all cancer patients. Radiation therapy is not curative in most cases, and the need for adjuvants is evident and unmet. There has emerged compelling evidence that radiotherapy is capable of inducing immunogenic cell death, which serves as a trigger for the immune system (“in situ vaccine”). Recently published preclinical and clinical data indicate that localized radiotherapy can evoke and/or modulate tumor-associated immune responses, resulting in systemic anti-tumor activity(1). There is generally a high expression of PDL-1 in HNSCC(2), and the expression is enhanced by RT. HNSCC is among the most radiation sensitive cancers, while also considered immunogenic, partly due to the high and increasing frequency of tumors infected with human papilloma virus (HPV)(2). Moreover, HNSCC with T-cell infiltration is more sensitive to radiotherapy.

In this study, the aim is to release the brake on the immune response by use of nivolumab, an inhibitory antibody against PD-1. Importantly, the immune response may not only boost local tumor control, but lead to eradication of metastatic disease and hence bring patients to a curative situation. Nivolumab has previously been shown to be effective in phase III trials in melanoma, lung cancer and renal cell carcinoma. Recently the results from a phase III study in HNSCC was reported(3). This was, an open-label, randomized study of nivolumab versus investigator’s choice of therapy in previously treated patients with HNSCC. The patients had tumor progression on or within 6 months of platinum therapy in the primary, recurrent, or metastatic setting. The trial randomized 361 patients 2:1 to receive either nivolumab 3 mg/kg intravenously every two weeks or investigator’s choice (cetuximab/methotrexate/docetaxel) until documented disease progression or unacceptable toxicity. The primary endpoint was OS. The study was stopped early due to positive interim results in favour of nivolumab. At the interim analysis, which was conducted after 218 events, patients assigned to nivolumab were found to have a 30 percent reduction in risk of death compared with those assigned therapy of investigator’s choice. Median overall survival was 7.5 months for those assigned nivolumab versus 5.1 months for those assigned therapy of investigator’s choice. At 12 months, 36 percent of the patients treated with nivolumab were alive compared with 17 percent of those assigned therapy of investigator’s choice. The response rate was 13.3% in the nivolumab group versus 5.8% in the standard-therapy group. The safety profile for nivolumab was favorable compared to the investigator’s choice therapy, and consistent with prior studies. Treatment-related adverse events of grade 3 or 4 occurred in 13.1% of the patients in the nivolumab group versus 35.1% of those in the standard-therapy group

Despite aggressive multimodal treatment with chemoradiotherapy, hypoxic-modulators and surgery to cure HNSCC patients, recurrent and second primary tumors in previous irradiated area (>46 Gy) are a common clinical challenge. Re-irradiation to doses of 60 Gy or more is a possible treatment option, offering long-term survival for selected patients. However, the re-irradiation is complicated with serious acute and late toxicity. Recurrent disease is also associated with a high risk of developing systemic disease. There is a need for new treatment approaches and combinations to improve tumor control and reduce toxicity.

Radiotherapy is a powerful inducer of inflammation, and the expression of PD1-L1 is known to be enhanced by inflammatory cytokines, including IFN γ . Experimental evidence from mice

models have shown that radiotherapy induces increased PD-L1 expression in tumor tissue. Moreover, there is evidence suggesting that HNSCC with T-cell infiltration is more sensitive to radiotherapy. There is thus a strong rationale for combining PD-1 inhibitors with radiotherapy. However, this potential remains largely unexplored in humans. We consider that head-and-neck cancer is a particularly attractive entity for investigating this therapeutic combination, because of i) the high radiosensitivity of this cancer form ii) the clinical efficacy of PD-1 inhibitors as monotherapy in early clinical trials iii) the availability of tumor biopsies for translational/biomarker research.

2.2 Nivolumab

Nivolumab is a fully human monoclonal antibody that binds to PD-1 with nanomolar affinity and a high degree of specificity, thus precluding binding of PD-1 to its ligands PD-L1 and PD-L2. Nivolumab does not bind other related family members, such as BTLA, CTLA-4, ICOS, or CD28. Nivolumab has been approved by FDA and EMA for treatment of metastatic melanoma, renal cell carcinoma (RCC) and NSCLC, based on phase III trials showing improved survival. Clinical trials have also demonstrated clinical activity of nivolumab against HNSCC (see above) and other cancers. Please refer to the Investigator's Brochure (IB)/approved labeling for detailed background information on nivolumab.

2.3 Rationale for Dose Selection

Nivolumab is safe and well tolerated up to 10 mg/kg Q2W dose level (see IB). The RT given in the present study gives considerable side effects, related to inflammation that may be enhanced by PD1 blockade. Nivolumab has shown efficacy and mild toxicity when given as monotherapy for HNSCC at a dose of 3.0 mg/kg Q2W, which is the target dose in the present trial(3). To assess the toxicity, the following dosing schedule has been chosen: Nivolumab, intravenous every 2nd week (1 cycle = 2 weeks), dose escalation schedule (1.0, 3.0 mg/kg), for a maximum of 12 months or until disease progression. RT will be given to a total dose of 60 Gy (1.5 Gy fractions twice daily) for a total period of 4 weeks. We expect that any increased toxicity will be observed within 2 weeks after end of RT and thus allow for a 3.0 mg/kg Q2W dose level thereafter. If a drug-related toxicity is observed, the guidelines outlined below will apply.

2.4 Risk/benefit considerations

The benefit-risk relationship has been carefully considered in the planning of the trial. Based on the preclinical and clinical data (see IB, (3) and above), the conduct of this trial is considered justifiable. Even though subjects in phase I/II clinical trials generally cannot expect to receive direct benefit, we believe the rationale for conducting this trial is sound, and it is a realistic chance that some patients could benefit from nivolumab in combination with radiotherapy. The routine treatment (i.e. radiotherapy or palliative chemotherapy alone) is not of major benefit for many patients in this group. The dose escalation schedule included in our trial design, and the moderate maximum dose of 3.0 mg/kg, mean that the risk of SAE related to nivolumab is limited. We thus consider that the risk-benefit ratio is favourable. Additional details regarding specific benefits and risks for subjects participating in this clinical trial may be found in the accompanying Investigators Brochure (IB) and Informed Consent documents.

3.0 SAFETY MONITORING COMMITTEE

A safety monitoring committee (SMC) will monitor safety on a periodic basis. Members of the

SMC will be experienced clinicians. The SMC will meet approximately every 6 months from the point of first patient in (FPI) to review safety and study conduct data. The safety data will include demographic data, adverse events and relevant laboratory data. In addition the SMC will meet after finalization of each dose cohort (i.e. three patients has completed minimum 8 weeks of treatment), and in case DLT is experienced. See section 8.8 for definitions.

Following each data review, the SMC will provide recommendations to the Study Leadership as to whether the study should continue or be amended, or whether the study should be stopped on the basis of safety (i.e., evidence of harm). The Study Leadership will make a decision on the basis of the SMC recommendations.

Any outcomes of these safety reviews that affect study conduct will be communicated in a timely manner to the investigators for notification of the Institutional Review Boards/Ethics Committees (IRBs/ECs).

No interim efficacy analysis is planned.

4.0 OBJECTIVES & HYPOTHESES

4.1 Objectives

Primary objectives:

- 1) To determine the safety and tolerability of nivolumab when administered concomitant with high dose (60 Gy) re-irradiation in patients with locally advanced recurrent or second primary HNSCC
- 2) To determine a safe dose of nivolumab when administered concomitant with high dose (60 Gy) re-irradiation in patients with locally advanced recurrent or second primary HNSCC

Secondary objectives:

- 1) To evaluate progression-free survival after 12 months
- 2) To evaluate objective response rate (ORR) and duration of response (DOR), by RECIST v1.1 as primary method and immune-related RECIST (irRECIST) as secondary method
- 3) To evaluate overall survival

Exploratory objectives:

- 4) To investigate the immunological response, tumor evolution and dynamics in the tumor microenvironment induced by the study therapy
- 5) To investigate biomarkers for development of clinical response, toxicity and immune response

4.2 Hypotheses

- Anti-PD1 mAb can safely be administered concomitant with re-radiation in HNSCC.

- The combination therapy can induce clinical response, immune response and dynamics in the tumor microenvironment.
- Genetical and immunological profiling of pre-treatment samples may identify biomarkers for predicting which patients will benefit from the therapy

5.0 METHODOLOGY

5.1 Entry Criteria

5.1.1 Subject Inclusion Criteria

- Age >18 years
- Recurrent or secondary primary squamous cell carcinoma originating from the oral cavity, oro/hypo-pharynx or larynx
- Prior radiotherapy (46-70Gy)
- Adequate newly obtained core or excisional biopsy of a recurrent tumor lesion
- Measurable disease
- Lesion available for biopsy during study treatment
- Eastern Cooperative Oncology Group (ECOG) performance status of 0 or 1
- Life expectancy > 12 months
- A minimum of 6 months since prior radiotherapy in the same area or minimum 4 weeks (28 days) since previous other cancer treatment
- Both HPV positive and HPV negative disease allowed
- Distant metastases allowed
- Adequate organ function based on clinical examination and lab values
- Women of childbearing potential (WOCBP) must have a negative serum or urine pregnancy test (minimum sensitivity 25 IU/L or equivalent units of HCG) within 24 hours prior to the start of study drug
- Women must not be breastfeeding
- WOCBP should use an adequate method to avoid pregnancy for 23 weeks (30 days plus the time required for nivolumab to undergo five half-lives) after the last dose of investigational drug
- Males who are sexually active with WOCBP must agree to follow instructions for method(s) of contraception for a period of 90 days (duration of sperm turnover) plus the time required for the investigational drug to undergo five half-lives. The terminal half-life of nivolumab is up to 25 days

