5.1.2 Subject Exclusion Criteria

- History of other prior malignancy, with the exception of curatively treated basal cell or squamous cell carcinoma of the skin, cervical cancer stage IB and stage I prostate cancer considered not necessary to treat
- Disease suitable for curative salvage surgery
- Treatment with any investigational medicinal product (IMP) that may interfere with the study treatment, within 4 weeks prior to first administration of study drug.

- Significant cardiac, pulmonary or other medical illness that would limit activity or survival
- Pregnancy or lactation.
- Known hypersensitivity to any of the components of the investigational product
- Patients who test positive for hepatitis B, C or HIV.
- Diagnosis of immunodeficiency or medical condition requiring systemic steroids or other forms of immunosuppressive therapy
- Autoimmune disease that has required systemic therapy within the past 2 years
- Any reason why, in the opinion of the investigator, the patient should not participate

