8.1.1.4 Prior and Concomitant Medications Review

8.1.1.4.1 Prior Medications

The Investigator or qualified designee will review prior medication use, including any protocol-specified washout requirement, and record prior medication taken by the subject within 28 days before starting the trial. Treatment for the disease for which the subject has enrolled in this study will be recorded separately and not listed as a prior medication.

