11.0 STATISTICAL ANALYSIS PLAN

11.1 Statistical Analysis Plan Summary

In this exploratory phase I study no formal hypothesis testing will be performed. Hence, the primary endpoint and secondary endpoints will be evaluated only by descriptive methods. Data will be described with proportions (percentage) for categorical data and with median, mean and range for continuous data. Kaplan-Meier curves will be produced for PFS and OS.

Progression free survival (PFS), defined as the time from inclusion to the occurrence of disease progression, as determined by investigators from tumor assessments per RECIST, or death from any cause, whichever occurs first. Data for patients without disease progression or death will be censored at the last tumor assessment date.

Overall survival (OS) will be calculated from the date of first dose of nivolumab until death. Patients alive at the time of data analysis will be treated as censored.

Exploratory analyses will be carried out to evaluate the data of the immunological and molecular analyses (e.g. biomarker studies) carried out. The statistical analyses will be dependent on the biological factors investigated and the analysis methodology used, and will be defined separately for each molecular study. With regard to some of the secondary/exploratory objectives, comparative analyses between groups or between samples obtained at different time points will be performed.

A number of 20 patients is considered suitable for addressing the primary endpoints, i.e. evaluating the safety and dose in the selected patient population. The biobank material obtained at consecutive time points from 20 patients should be sufficient for informative collateral studies.

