16.4.2 Tumor response evaluation

16.4.2.1 Definitions of target/non-target lesions

Target Lesions

When more than one measurable lesion is present at baseline, all lesions up to a maximum of five lesions total (and a maximum of two lesions per organ) representative of all involved organs should be identified as target lesions and will be recorded and measured at baseline. This means that, for instances in which patients have only one or two organ sites involved, a maximum of two lesions (one site) and four lesions (two sites), respectively, will be recorded. Other lesions (albeit measurable) in those organs will be recorded as non-measurable lesions (even if the size is >10 mm by CT scan).

Target lesions should be selected on the basis of their size (lesions with the longest diameter) and be representative of all involved organs, but in addition, should lend themselves to reproducible repeated measurements. It may be the case that, on occasion, the largest lesion does not lend itself to reproducible measurement, in which circumstance, the next largest lesion that can be measured reproducibly should be selected.

Lymph nodes merit special mention since they are normal anatomical structures that may be visible by imaging even if not involved by tumor. As noted above, pathological nodes that are defined as measurable and may be identified as target lesions must meet the criterion of a short axis of ≥ 15 mm by CT scan. Only the short axis of these nodes will contribute to the baseline sum. The short axis of the node is the diameter normally used by radiologists to judge if a node is involved by solid tumor. Nodal size is normally reported as two dimensions in the plane in which the image is obtained (for CT, this is almost always the axial plane; for MRI, the plane of acquisition may be axial, sagittal, or coronal). The smaller of these measures is the short axis. For example, an abdominal node that is reported as being 20 mm \times 30 mm has a short axis of 20 mm and qualifies as a malignant, measurable node. In this example, 20 mm should be recorded as the node measurement. All other pathological nodes (those with short axis ≥ 10 mm but < 15 mm) should be considered non-target lesions. Nodes that have a short axis of < 10 mm are considered non-pathological and should not be recorded or followed.

Lesions irradiated within 3 weeks prior to Cycle 1 Day 1 may not be counted as target lesions.

Non-Target Lesions

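### The entry criterion joins the 6-month re-irradiation interval and the 28-day washout with *or*, so read literally either one is enough

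*Combined protocol and SAP*

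**What the plan says.** The inclusion list in section 5.1.1 has a single bullet on time since earlier treatment: "A minimum of 6 months since prior radiotherapy in the same area or minimum 4 weeks (28 days) since previous other cancer treatment". A separate bullet in the same list makes earlier radiotherapy in the 46 to 70 Gy range mandatory, without giving an interval. Section 5.2 then gives every patient a further 60 Gy.

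The nearest other washout rule is an exclusion in section 5.1.2: "Treatment with any investigational medicinal product (IMP) that may interfere with the study treatment, within 4 weeks prior to first administration of study drug". It is confined to investigational products. Section 5.1.2 also has a discretionary exclusion: "Any reason why, in the opinion of the investigator, the patient should not participate".

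The first primary objective in section 4.1 is "To determine the safety and tolerability of nivolumab when administered concomitant with high dose (60 Gy) re-irradiation"; the second is to find a safe nivolumab dose in the same setting. Section 2.1 acknowledges that re-irradiation carries serious acute and late toxicity.

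**The concern.** An inclusion criterion is applied as written by the person screening and by the monitor. Here the connective is *or*, and elsewhere in the same list *or* offers alternatives of which one is enough: recurrent or second primary tumour, core or excisional biopsy, performance status 0 or 1, serum or urine pregnancy test. Read the same way, this bullet lets a patient satisfy the 28-day limit and skip the 6-month one, or the reverse.

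The first of these matters more. Section 9.8 expects dose-limiting dermatitis and mucositis, which are also plausible effects of re-irradiation. A toxicity driven by a short radiotherapy interval could therefore be attributed to nivolumab. During escalation there are only three patients per dose level. The Grade 4 rule in section 9.8 lowers the dose by one level after a single event, and that sentence sets no condition of relatedness to nivolumab. The Grade 3 rule is stricter: it needs a possibly nivolumab-related event and then the same event in a second patient (2 of 4). One patient enrolled on the loose reading could thus influence the dose decision.

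**Working it through.** The plan gives no figure to reproduce. The check is one of logic and of reading across the protocol, followed by simple arithmetic for scale.

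**1. The two readings.** Let A be at least 6 months since same-area radiotherapy, and B at least 28 days since other cancer treatment, for a patient who has had both.

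| A met | B met | Bullet as written (*or*) | Both required |
|---|---|---|---|
| yes | yes | eligible | eligible |
| yes | no | eligible | not eligible |
| no | yes | eligible | not eligible |
| no | no | not eligible | not eligible |

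The text admits three of the four combinations; requiring both admits one. These are logical cases, not proportions of patients. Radiotherapy two months ago with chemotherapy five weeks ago is the third row. The readings differ only for patients who have had both kinds of treatment, but section 2.1 describes a population treated with chemoradiotherapy, hypoxic modulators and surgery, so such patients are within it.

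**2. Does another section supply the missing requirement?**

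- Section 1.0 (summary), section 2.1 (background), section 5.2 (treatment) and section 7.0 (flowchart) give no minimum interval from earlier radiotherapy.
- Section 5.1.2: the 4-week exclusion covers interfering investigational products only.
- Section 8.1.1.2: all criteria are to be reviewed, which means the bullet as it stands.
- Section 8.1.1.4.1: prior medication is reviewed, "including any protocol-specified washout requirement", with no interval given.
- Section 8.1.1.5.2: all prior cancer treatments are reviewed, with no interval given.
- Section 8.1.3.2: screening refers back to section 5.1.
- Section 16.4.2.1: "Lesions irradiated within 3 weeks prior to Cycle 1 Day 1 may not be counted as target lesions". This concerns the choice of target lesions, not eligibility.

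None requires both limits.

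**3. How far apart the readings can be.** Assumption, for illustration only: same-area radiotherapy and concurrent chemotherapy ended on the same day, and the chemotherapy counts as other cancer treatment.

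- Intended minimum: 365.25 / 2 = 182.6 days
- Literal minimum: 28 days
- Difference: 182.6 − 28 = 154.6 days, and 154.6 / 30.44 = 5.1 months

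**4. Where the dose rules apply.** Section 5.2 plans 20 patients, with three at each of two dose levels before any additions.

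- Escalation: 3 × 2 = 6 patients, 6 / 20 = 30%
- With one patient added at one level: 7 / 20 = 35%; with one added at each level: 8 / 20 = 40%
- After escalation, with no additions: 20 − 6 = 14 patients

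For those treated after escalation, section 9.8 calls for a safety committee meeting and a pause in inclusion, not an automatic dose reduction. It does so after two patients with Grade 3 events or one with a Grade 4 event considered related to nivolumab.

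**The case against.** The best answer is that the bullet has a sensible reading that most investigators would adopt. The word *other* divides earlier therapy into same-area radiotherapy and everything else, each with its own limit, and *or* merely lists the two cases. The literal reading would let a patient irradiated last week qualify because surgery was five weeks ago, and an investigator choosing patients for 60 Gy is unlikely to accept that. Several steps also narrow the path: review of all earlier treatments (section 8.1.1.5.2), calculation of dose to organs at risk (section 5.2), a newly obtained biopsy of recurrent tumour and a life expectancy above 12 months (section 5.1.1), the rule that lesions in an irradiated area usually count as measurable only after shown progression (section 16.3.1), and the discretionary exclusion. Harm would need a chain of events whose probability nobody can state.

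Most of this stands. The distributive reading is probably what was meant, short-interval enrolment may be uncommon, and neither the 155 days nor the 30% measures how often the ambiguity would matter. What does not follow is that the wording is sound. The safeguards are indirect or discretionary and none sets a radiotherapy interval. Monitoring (section 13.3) and deviation recording (section 13.2) work from the text, and under the text a short-interval patient is not a clear deviation.

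**Conclusion.** The concern holds, as a minor correction. The bullet, followed exactly, gives the wrong result for patients who have had both same-area radiotherapy and other cancer treatment, and nothing else in the protocol corrects it. It is the only minimum interval stated before 60 Gy re-irradiation, in a trial designed to establish safety and dose.

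No frequency or toxicity effect is claimed, because the documents support neither. The gap of about 155 days rests on the same-day assumption. The direct effect on dose is confined to the escalation phase, about 6 of the 20 planned patients before additions. Neither interval is disputed, and no specific hazard is claimed from the 28-day limit being skipped.

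**What to change.** Replace the bullet in section 5.1.1 with two criteria, both of which must be met:

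- (a) at least 6 months since prior radiotherapy in the same area; and
- (b) at least 28 days since any other cancer treatment, if given.

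The final condition in (b) matters: simply changing *or* to *and* would leave patients with no other treatment unaddressed. The cost is one line of protocol wording. Both intervals, the sample size and the descriptive analysis stay as they are.
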